7.1.2 GEE model

CGI-I and the change from baseline of CGI-S endpoints will be analyzed using an GEE model. Treatment arm and stratification factors as fixed effects and baseline response as a covariate. The model will also include a repeated statement that allows to model the correlation of the dependent variable at different time points.

An ordinal multinomial distribution with cumulative logit link is assumed in the model. Parameter estimates, standard errors and 95% confidence intervals will be presented which are based on empirical standard error estimates.

The following provides sample code for implementing GEE analysis using independent covariance matrix:

```
proc genmod data=test descending;
  class subjid trt visit agegr antipmed region;
  model chg = base trt visit trt*visit base*visit randager randrgn randpsy /
  dist=multinomial
  link=clogit type3 wald;
  repeated subject=subjid / withinsubject=visit type=indep corrw covb;
```

Note: Model variables are same as in MMRM

7.1.3 Logistic regression model

The proportion of responders of CGI-I endpoint will be analysed using logistic regression. Treatment, stratification variables, and baseline score will be included as covariates. The odds ratio between treatment groups and its 95% confidence intervals at Week 12 will be presented. The following provides sample code for implementing logistic regression:

```
ods output oddsratios=ors parameterestimates=params;
proc logistic data=test descending;
  class trt randager randrgn randpsy/ param=ref;
  model response = base trt randager randrgn randpsy;
run;
where, response is the response variable.
```

7.1.4 ANCOVA model

An ANCOVA model with randomization stratification factors and treatment arm as factors and baseline score as a covariate will be used to analyze change from baseline to Week 12. The LS mean estimates for each treatment arm will be displayed together with standard errors and their corresponding 95% CIs. Treatment differences with 95% CIs will also be produced.

The following provides sample code for implementing ANCOVA analysis:

```
ods output lsmeans=lsmeans diffs=diffs;
proc mixed data=test;
  class trt randager randrgn randpsy;
  model chg = base trt randager randrgn randpsy / ddfm=kr cl
  alpha=0.05 solution;
  lsmeans trt / cl diff;
run;
```

7.1.5 Bayesian analysis

Bayesian analysis on the final data will be carried out as described in interim analysis plan.

7.2 Efficacy endpoints

7.2.1 Vineland Adaptive Behavior Scales, 3rd Edition (VABS-3)

The Vineland-3 assesses adaptive behavior in 3 domains: Communication, Daily Living Skills, and Socialization. Each domain has 3 subdomains: receptive, expressive, written (Communication domain); personal, domestic, community (Daily Living Skills domain); interpersonal relationships, play and leisure, coping skills (Socialization domain). The assessment are done at Visit 2, Visit 5, Visit 7, and Visit 8 EoT/WD.

Subdomain and domain scores will be calculated in the Rater Station. The Chronological Age at baseline is used to derived scores for the Vineland-3 throughout the study. The social and communication composite score is a key interest and will be calculated as the arithmetic mean of the Socialization and Communication domain scores.

The adaptive behavior composite score is calculated as arithmetic mean of all 3 domain scores.

The change from baseline in subdomain, domain and composite scores will be summarized by visit. The change from baseline in social and communication composite score, adaptive behavior composite score, and individual domain scores will be analyzed using an MMRM model. Multiple analyses will carryout by including all observed data and using per protocol set. Normality assumption will be tested for Social and communication composite using Q-Q plot.

7.2.2 Aberrant Behavior Checklist (ABC)

The ABC contains items that resolve into 5 subscales: Irritability (15 items); Social Withdrawal (16 items); Stereotypic Behavior (7 items); Hyperactivity/Noncompliance (16 items); and Inappropriate Speech (4 items). Each item is scored as 0 (never a problem), 1 (slight problem), 2 (moderately serious problem), or 3 (severe problem). The assessment is done by the caregiver at Visit 1 (Screening), Visit 2, Visit 5, Visit 7, and Visit 8 EoT/WD.

Subscale score is calculated as the sum of the items belonging to each subscale. ABC-I (Irritability) subscale score is of the key interest.

Subscale	Items
ABC-I (Irritability)	2, 4, 8, 10, 14, 19, 25, 29, 34, 36, 41, 47, 50, 52, 57
Social Withdrawal	3, 5, 12, 16,, 20, 23, 26, 30, 32, 27, 40, 42, 43, 53, 55, 58
Stereotypic Behavior	6, 11, 17, 27, 35, 45, 49
Hyperactivity/Noncompliance	1, 7, 13, 15, 18, 21, 24, 28, 31, 38, 39, 44, 48, 52, 54, 56
Inappropriate Speech	9, 22, 33, 46

The change from baseline in ABC-I and other subscale scores will be summarized by visit. MMRM analysis as described in Section 7.2 will be used to analyze the change from baseline in ABC-I and other subscale scores.

Multiple analyses will carryout by including all observed data and using per protocol set. Normality assumption will be tested for ABC-I (irritability) score using Q-Q plot.

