9.1.11.4 Aberrant Behavior Checklist

The ABC was designed to assess the presence and severity of various problem behaviors commonly observed in individuals diagnosed with intellectual and developmental¹⁶. It contains items that resolve onto 5 subscales: Irritability (15 items); Social Withdrawal (16 items); Stereotypic Behavior (7 items); Hyperactivity/Noncompliance (16 items); and Inappropriate Speech (4 items). Each item is scored as 0 (never a problem), 1 (slight problem), 2 (moderately serious problem), or 3 (severe problem).

The ABC will be completed by the caregiver.

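### The SAP's ABC scoring table puts items 27 and 52 in two subscales each and items 37 and 51 in none, so at least two subscale scores, possibly including ABC-I, would be wrong

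*SAP*

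**What the plan says.** Protocol 9.1.11.4 and SAP 7.2.2 agree that the ABC resolves into five subscales: Irritability (ABC-I) with 15 items, Social Withdrawal with 16, Stereotypic Behavior with 7, Hyperactivity/Noncompliance with 16 and Inappropriate Speech with 4. Each item is scored from 0 to 3. The protocol gives no item numbers.

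The SAP gives the scoring rule, "Subscale score is calculated as the sum of the items belonging to each subscale", followed by a table of item numbers. Four of its rows matter here, in two pairs:

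- Item 27 is shared by two rows. The first of them, for Social Withdrawal, reads "3, 5, 12, 16,, 20, 23, 26, 30, 32, 27, 40, 42, 43, 53, 55, 58", with 27 out of numerical order. The second, for Stereotypic Behavior, is the short list "6, 11, 17, 27, 35, 45, 49", where 27 is in its numerical place.
- Item 52 is also shared by two rows. One is the Hyperactivity/Noncompliance row, given as "1, 7, 13, 15, 18, 21, 24, 28, 31, 38, 39, 44, 48, 52, 54, 56", and here the order is ascending throughout. The other is the row for the key subscale, ABC-I, given as "2, 4, 8, 10, 14, 19, 25, 29, 34, 36, 41, 47, 50, 52, 57", again in ascending order.

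The remaining row, for Inappropriate Speech, has items 9, 22, 33 and 46. No other section of either document gives an item key.

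Change from baseline to Week 12 in the ABC subscales is an efficacy endpoint (SAP Table 1). Protocol 13.6.1.2 and SAP 7.2.2 both single out ABC-I as being of key interest.

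**The concern.** If 58 items resolve into five subscales whose sizes add to 58, each item should belong to exactly one subscale. The table breaks this: two items serve two subscales each and two items serve none.

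A derivation program written to the table would include a wrong item and leave out a right one in at least two subscales, at baseline and at every later visit. It would also feed one item into two endpoints that are meant to be distinct. Because every row has the stated number of entries, a check of row lengths would not reveal the fault. Independent double programming from the same table would reproduce it.

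ABC-I has the most at stake. It is named in the clinical hypothesis (Protocol 3.4), it informed the sample size (Protocol 13.1), and a score of at least 15 at screening is an entry criterion (Protocol 6.1.7). If the ABC-I row is one of the faulty ones, the analysed key endpoint is not the standard subscale. It would also differ from the entry score if that score was taken from the instrument's own key.

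**Working it through.** **Inputs.** The stated subscale sizes are from SAP 7.2.2 and Protocol 9.1.11.4. The item lists, the 0–3 item range and the summation rule are from SAP 7.2.2. The ABC-I planning values are from Protocol 13.1.

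**Step 1: reproduce the stated counts.**

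| Subscale | Stated items | Entries listed | Row in ascending order? |
|---|---|---|---|
| ABC-I | 15 | 15 | yes |
| Social Withdrawal | 16 | 16 | no (27 stands between 32 and 40) |
| Stereotypic Behavior | 7 | 7 | yes |
| Hyperactivity/Noncompliance | 16 | 16 | yes |
| Inappropriate Speech | 4 | 4 | yes |
| Total | 58 | 58 | |

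The counts agree. The double comma after 16 in the Social Withdrawal row therefore hides no lost item.

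**Step 2: check whether the rows use each of 1–58 once.** Tallying the 58 entries gives 56 distinct numbers.

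- Listed twice: 27 (Social Withdrawal, Stereotypic Behavior) and 52 (ABC-I, Hyperactivity/Noncompliance).
- Listed nowhere: 37 and 51.
- The other 54 items appear once each.

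A cross-check by sums: the numbers 1 to 58 add to 58 × 59 / 2 = 1711. The five rows add to 428 + 485 + 190 + 489 + 110 = 1702. The shortfall of 9 equals (37 + 51) − (27 + 52) = 88 − 79.

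**Step 3: find the corrections that restore the partition.** One copy of 27 and one copy of 52 must be replaced by 37 and 51. There are 2 × 2 × 2 = 8 ways: which row gives up 27, which gives up 52, and which missing number goes where. Each way changes exactly two subscales. Only two of the eight leave every row in ascending order. Both put 37 in place of 27 in Social Withdrawal. They differ on 52:

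- 51 replaces 52 in ABC-I (…50, 51, 57), or
- 51 replaces 52 in Hyperactivity/Noncompliance (…48, 51, 54).

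Nothing in the documents decides between these two.

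**Step 4: size for one patient.** The error in an affected score is (wrong item − right item), which lies between −3 and +3. That is 3 of 48 points on a 16-item subscale and 3 of 45 on ABC-I. For change from baseline, the difference of two such errors lies between −6 and +6.

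**Step 5: size for the treatment effect.** This step assumes that all items contribute equally to the effect and that the wrong item carries none of it. The fraction lost is then 1/16 = 6.25% for Social Withdrawal or Hyperactivity/Noncompliance, and 1/15 = 6.7% for ABC-I. On the planned ABC-I difference of 8.26 points this is 8.26/15 ≈ 0.55, leaving about 7.71. If the wrong item responds as much as the right one, the loss is zero.

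**Step 6: effect on the planned ABC-I power.** With SD 8.27 and 72 per arm, the standard error is 8.27 × √(2/72) = 1.378. Power at a difference of 8.26 is Φ(8.26/1.378 − 1.96) ≈ 0.99997, which reproduces the protocol's figure of more than 99%. At 7.71 it is Φ(7.71/1.378 − 1.96) ≈ Φ(3.63), still above 0.999.

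**The case against.** The tally itself is not open to dispute. The case on the other side concerns consequences.

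- **The harm is conditional.** The SAP's rule refers to the items that belong to a subscale, the protocol cites the ABC manual, and questionnaires are captured on electronic devices (SAP 4.1). Scores might come from a correct built-in key. This stands as a condition. But SAP 7.2.1 says that VABS-3 scores come from the Rater Station, whereas 7.2.2 names no outside scoring for the ABC and supplies a list and a summation rule. If a vendor's key is used after all, the SAP misdescribes what is analysed.
- **Harm to ABC-I is unproven.** This stands. Item 51 fits the ABC-I row and the Hyperactivity/Noncompliance row equally well. The link to the entry criterion is likewise only a possibility, because the documents do not say how the screening score is derived.
- **The numerical effect is modest.** This stands in part. The 6–7% rests on simplifying assumptions, power for the planned ABC-I difference barely moves, and one key applied to both blinded arms favours neither. The trial is exploratory and draws no inferential decision. Even so, a score built from the wrong items is not the stated endpoint.
- **A misread digit in the PDF text could create this pattern.** This cannot be fully excluded. An author's slip is at least as plausible, since the SAP has other typing errors, and checking the source table costs nothing.

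**Conclusion.** The concern holds. As written, the table does not assign each ABC item to one subscale: 27 and 52 are used twice, and 37 and 51 are never used. Scores derived from it are wrong for one of Social Withdrawal and Stereotypic Behavior (the ordering points to Social Withdrawal), and for one of ABC-I and Hyperactivity/Noncompliance (undetermined).

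The conclusion rests on two inferences: that items are numbered 1 to 58, and that each belongs to one subscale. Both are well supported, because the subscale sizes sum to 58, the highest number listed is 58, and both documents describe the items as resolving into five subscales.

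The likely effect on group comparisons is modest and the stated ABC-I power is not in question. The point must still be fixed, because it is a definite error in an endpoint definition and the SAP alone cannot rule out that ABC-I is mis-scored.

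**What to change.** Correct the table in SAP 7.2.2 against the ABC manual cited in the protocol, so that each of items 1–58 appears exactly once. The expected changes, to be confirmed there, are 37 for 27 in Social Withdrawal, and 51 for 52 in whichever of ABC-I or Hyperactivity/Noncompliance the manual indicates. State in the SAP whether subscale scores are derived from this table or supplied by the electronic questionnaire system. Confirm that the screening ABC-I score uses the same key.

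Add a check to the derivation program that the five lists do not overlap and together cover 1–58. A check of row lengths alone would pass the present table.

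The cost is a small edit to the table and to the program, with no effect on data collection or sample size. It should be made before unblinding, since re-scoring a key endpoint afterwards could look data-driven.

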7.2.3 Clinical Global Impression – Severity and Improvement (CGI-S and CGI-I)

The CGI-S is a 7-point scale that requires the clinician to rate the severity of the patient's illness at the time of assessment, relative to the clinician's experience with patients who have the same diagnosis. The clinician is asked: *Considering your total clinical experience with this particular population, how ill is the patient at this time?* This is rated as: 1 = normal, not at all ill; 2 = borderline ill; 3 = mildly ill; 4 = moderately ill; 5 = markedly ill; 6 = severely ill; or 7 = extremely ill. The questionnaire is done at Visit 1 (Screening), Visit 2, Visit 5, Visit 7 and Visit 8 EoT/WD.

The CGI-I is a 7-point scale that requires the clinician to assess how much the patient's illness has improved or worsened relative to a baseline state at the beginning of the intervention. The clinician is asked: *Compared to the patient's condition at admission to the project, how much has the patient changed?* This is rated as: 1 = very much improved; 2 = much improved; 3 = minimally improved; 4 = no change; 5 = minimally worse; 6 = much worse; or 7 = very much worse.

The questionnaire is done at Visit 5, Visit 7 and Visit 8 EoT/WD.

[figure not shown]
The frequency and proportions of patients within each category for the CGI-S and CGI-I scores will be produced separately by visit.

A GEE model will be fitted, for CGI-I (or change from baseline CGI-S) as the dependent variable, visit, treatment arm, stratification factors, baseline into visit interaction and treatment

into visit interaction as fixed effects and baseline response (CGI-S for both models) as a covariate.

Patients who achieve a score of 1 or 2 ('very much' or 'much' improved) on the CGI-I scale at Week 12 will be considered responders and the rest are considered non-responders. A logistic regression model will be used for analysing the responses. A second analysis similar to above will be done with subjects who achieve a score of 1, 2 or 3 ('very much', 'much', 'minimally' improved) at Week 12.

8. Safety Analyses

Safety analyses will use data from the Safety analysis set. For each safety analysis endpoint, GWP42003-P will be compared with placebo in all sections to follow.

8.1 Exposure and treatment compliance

Exposure

Exposure to GWP42003-P or placebo will be summarized using the following parameters:

- Treatment duration, calculated as the number of days subject received study drug, using the formula:
 - (the date of the last dose the date of the first dose +1). [CFR data]
 - Treatment duration will be summarized overall and separately for treatment and taper period.
- Average dose (mg/kg/day) based on diary reported days by visit and overall

Diary compliance

Diary compliance (%) is calculated by:

Diary entries * 100/ expected diary entries.

Expected diary entries are derived from treatment duration.

Dose compliance based on Diary

Number of doses administered, as reported in the diary, and dose compliance percentage will be summarized overall and separately for treatment and taper period

Dose compliance based on Diary (%) is calculated by:

Number of doses administered * 100/ number of diary entries (am+pm)

Dose compliance based on CRF

Total expected volume since last dispensation, total volume actually taken since last dispensation and derived dose compliance (%) are captured on CRF at Visit 5, Visit 8 EoT/WD, and Visit 9/End of Taper; derived dose compliance will be summarized for each period.

Number and percentage of subjects compliant will be summarized for each period by treatment group and overall for following groups;

Compliant: ≥75% to ≤125%

Minor Compliance Deviations 50-75 & 125-50 Major Compliance deviations: <50 and >150

Consistency of dose administration in relation to meal timing (Yes, No) by visit will be summarized separately.

Dose adjustment and suspension

The number and percent of subjects with any dose adjustment (overall and by reason) as collected on Investigator Dose Adjustment CRF will be summarized.

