8.1.2 Dose Escalation, Adjustments, and Taper

Patients will be administered 5 mg/kg/day GWP42003-P or matching volumes of placebo for 1 week and then 10 mg/kg/day GWP42003-P or matching volumes of placebo for 11 weeks.

If an unacceptable AE develops at any time during the dose escalation or treatment periods, dosing should be reduced, at the investigator's discretion and in a blinded manner, until the event has resolved or is well tolerated. The end of treatment taper schedule should be used to guide dose adjustment. If required, dosing may be suspended. Patients whose dose has been decreased should have their dose increased again, if the tolerability improves. Patients unable to tolerate the target dose may stay at a lower dose. If a patient cannot tolerate a dose of 5 mg/kg/day, the investigator should discuss with the medical monitor whether patient continuation in the trial is recommended. Single dose volumes must be at least 0.1 mL.

Transaminase elevations should be medically managed by the investigator either by reducing the IMP dose or, following discussion with the medical monitor, by reducing concomitant medications judged to be causing the elevation (as per Section 10). For potential cases of drug-induced liver injury see Section 12.9.

Dose adjustments should be discussed with the GW medical monitor. The final decision regarding dose adjustments should be taken by the investigator.

At the end of treatment, patients will taper the medication in steps of -2.5 mg/kg/day every 2 days.

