If the severity of an AE fluctuates day-to-day, e.g., a headache or constipation, the change in severity should not be recorded each time; instead, only the worst observed severity should be recorded with AE start and stop dates relating to the overall event duration, regardless of severity.

A severe AE is not the same as a SAE. For example, a patient may have severe vomiting, but the event does not result in any of the SAE criteria above. Therefore, it should not be classed as serious.

The severity of an AE will be recorded as one of the following:

- Mild: easily tolerated, does not interfere with normal daily activities, does not require intervention.
- Moderate: causes some interference with daily activities; minimal, local or non-invasive intervention indicated.
- Severe: daily activities limited or completely halted; intervention indicated.

E) Causality

See Section 12.6 above.

F) Action Taken with Trial Medication

This question refers to the action taken with the IMP due to an AE. The action with the IMP must be classed as:

- Dose Not Changed.
- Dose Reduced.
- Drug Interrupted.
- Drug Withdrawn.

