- TEAEs leading to withdrawal of IMP by SOC and PT. This subset includes TEAEs with an Action Taken of "Drug Withdrawn." Withdrawal means permanent discontinuation of IMP.
- Treatment related TEAEs leading to withdrawal of IMP by SOC and PT. This subset includes TEAEs with an Action Taken of "Drug Withdrawn." Withdrawal means permanent discontinuation of IMP.
- TEAEs leading to dose reductions by SOC and PT. This subset includes TEAEs with an Action Taken of "Dose Reduced."
- TEAEs related to treatment leading to dose reductions by SOC and PT. This subset includes TEAEs with an Action Taken of "Dose Reduced."
- TEAEs leading to dose reductions and are resolved by SOC and PT. This subset includes TEAEs with an Action Taken of "Dose Reduced" and Outcome "Recovered/Resolved" or "Recovered/Resolved with Sequelae".
- TEAEs leading to dose interruptions by SOC and PT. This subset includes TEAEs with an Action Taken of "Dose Interrupted."
- TEAEs related to treatment leading to dose interruptions by SOC and PT. This subset includes TEAEs with an Action Taken of "Dose Interrupted."
- TEAEs leading to dose interruptions and are resolved by SOC and PT. This subset includes TEAEs with an Action Taken of "Dose Interrupted" and Outcome "Recovered/Resolved" or "Recovered/Resolved with Sequelae".
- Fatal TEAEs by SOC and PT. This subset includes TEAEs with Outcome "Fatal".

 Treatment-emergent AESIs by SOC and PT. The definition of AESI is described in Section 8.1.3.

The following AE listings will be prepared:

- All AEs
- Serious TEAEs
- TEAEs related to treatment
- TEAEs leading to drug withdrawal
- Fatal TEAEs
- Treatment-emergent AESIs

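### SAP 8.1 describes treatment duration as days on drug but computes the span from first to last dose, so suspended days before resumption count as dosed

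*SAP*

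**What the plan says.** **Duration.** SAP 8.1 opens the exposure summary with "Treatment duration, calculated as the number of days subject received study drug, using the formula". The formula takes the dates of the last and first dose and adds 1. The result is summarized overall and separately for the treatment and taper periods.

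**Suspension.** Protocol 8.1.2, on handling an unacceptable adverse event, says "If required, dosing may be suspended". Protocol 12.6 F has an interruption category separate from permanent withdrawal, so a pause followed by resumption is foreseen.

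**What depends on duration.** For diary compliance, SAP 8.1 says "Expected diary entries are derived from treatment duration". Diary dose compliance is different: it divides doses administered by the morning and evening entries actually made.

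**Counting of suspensions.** Under a heading that names both dose adjustment and suspension, SAP 8.1 says: "The number and percent of subjects with any dose adjustment (overall and by reason) as collected on Investigator Dose Adjustment CRF will be summarized". It mentions neither a separate count of suspensions nor their length.

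**Interruption tables.** Protocol 12.6 F lists four actions taken with trial medication. The one for a pause is "Drug Interrupted". The three interruption tables in SAP 8.2 select on *Dose Interrupted* instead. The SAP's filters for reduction and withdrawal match the protocol's terms.

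**The concern.** The description and the formula agree only when dosing is never paused. Once a patient stops and restarts, the formula returns elapsed time while the label promises days on which drug was taken. A reader of the exposure table would take the figure at its label.

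The same span then sets the denominator of diary compliance, where the error works in the opposite direction. A caregiver who correctly makes no entries during an ordered pause appears to have missed some. One pause can thus make exposure look more complete and diary-keeping look worse.

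What is at stake is the description of exposure and adherence in a trial with a single target dose. Protocol 13.6.3.1 requires compliance and exposure to be summarized, and these tables should mean what they say.

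**Working it through.** The plan gives no figure for this quantity, so there is none to reproduce. The check applies the SAP formula to a planned course with a pause inside it.

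**Inputs**
- Planned treatment period, taper excluded: 1 week + 11 weeks = 12 × 7 = 84 days (protocol 8.1.2, SAP 3.5).
- Dosing twice daily, with morning and evening diary entries (protocol 8.1.1, SAP 8.1). Expected entries are taken as 2 per day of the span. That the first dose is an evening dose is ignored.
- Length of suspension, *s* days: an **assumption**, since the documents give neither lengths nor a limit. Range used: 3 to 28 days.
- The minus sign in the formula is absent from the extracted text. It is read as lost in extraction and is not part of this point.

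**One patient who suspends and resumes**
- SAP formula: last − first + 1 = 84 for every *s*.
- Days on drug: 84 − *s*.
- Relative overstatement: *s* / (84 − *s*).
- Diary compliance if no entries are made during the pause: 2(84 − *s*) / (2 × 84).

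| *s* (assumed) | Formula | Days on drug | Overstatement | Diary compliance, no entries in pause |
|---|---|---|---|---|
| 3 | 84 | 81 | 3/81 = 3.7% | 162/168 = 96.4% |
| 7 | 84 | 77 | 7/77 = 9.1% | 154/168 = 91.7% |
| 14 | 84 | 70 | 14/70 = 20.0% | 140/168 = 83.3% |
| 28 | 84 | 56 | 28/56 = 50.0% | 112/168 = 66.7% |

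**How the diary is filled in matters.** If no entries are made during the pause, diary dose compliance is 2(84 − *s*) / 2(84 − *s*) = 100%, and the pause shows only as lower diary compliance. If zero-dose entries are made, diary compliance is 168/168 = 100% and dose compliance takes the values in the last column. Protocol 8.4 has the caregiver record the volume on each treatment day, which does not settle which of the two happens.

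**Arm mean.** If a proportion *p* of patients have a resumed suspension averaging *s* days, the mean is overstated by *p* × *s* days. With *p* = 10% (also an assumption):
- *s* = 7: 0.1 × 7 = 0.7 days; 0.7 / (84 − 0.7) = 0.8%.
- *s* = 28: 0.1 × 28 = 2.8 days; 2.8 / (84 − 2.8) = 3.4%.

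**Boundary.** A suspension that becomes permanent ends at the last dose and is not overcounted.

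**Category names.** Protocol 12.6 F: Dose Not Changed, Dose Reduced, Drug Interrupted, Drug Withdrawn. SAP 8.2 filters: Dose Reduced (in the list), Drug Withdrawn (in the list), Dose Interrupted (not in the list).

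**The case against.** The best defence is that duration is one descriptive parameter among several. SAP 8.1 also plans average dose in mg/kg/day, number of doses administered, and CRF dose compliance from the volume actually taken. None of these uses the duration formula directly, and volume taken answers the question of how much drug was received better than duration does. This largely stands and limits the consequence. It is not a complete safeguard: average dose rests on diary-reported days, so a pause without entries drops out of it, and the SAP does not say whether expected volume is reduced during a suspension.

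Four stronger readings are tempting, and the documents do not support them:

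- *The interruption tables will be empty.* A literal filter on the protocol's list would select no records. But the eCRF code list is not shown, the protocol has only one interruption category, and the mismatch is probably a wording slip.
- *Efficacy or safety comparisons are biased.* The efficacy models in SAP 7.1 do not use duration, and the adverse event tables in SAP 8.2 are counts and percentages of patients, not exposure-adjusted rates. SAP 5.2.4 allows per-protocol exclusion for noncompliance but does not tie it to diary compliance.
- *The overstatement is larger on active drug.* More tolerability pauses on active drug are plausible, but the documents give no suspension frequency for either arm.
- *Suspensions are not counted at all.* The paragraph's heading names suspension, and protocol 8.1.2 treats suspension within dose adjustment. The count of any dose adjustment may already include it. The form is not shown, so this needs confirming.

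**Conclusion.** The point holds as an inconsistency between definition and formula. For a patient who suspends and resumes, the SAP formula overstates days on drug by exactly the suspended days. The direction and mechanism follow from the text alone. The sizes rest on assumed lengths: 3.7% to 50.0% in one patient for 3 to 28 days, and about 0.8% in an arm mean if 10% of patients had a 7-day suspension. With the true frequency unknown, the effect on an arm may be small.

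Diary compliance is understated through the same span, on the condition that no entries are made during the pause. The error is confined to descriptive exposure and diary-compliance summaries. The category name in the interruption tables is a separate, minor misalignment that should be removed because the correction is trivial.

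**What to change.** In SAP 8.1:
1. Keep last dose date minus first dose date plus 1, but label it time from first to last dose.
2. Add days on drug = that span minus suspended days, overall and for the treatment and taper periods. Name the source of suspended days: the diary or the Investigator Dose Adjustment CRF.
3. State how suspended days enter expected diary entries. If no entries are required during a suspension, remove those days from the denominator; if zero-dose entries are required, keep them and say so.
4. Report by arm the number of patients with a suspension and the days suspended. Confirm whether the count of any dose adjustment already includes suspensions.

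In SAP 8.2, replace *Dose Interrupted* with the protocol 12.6 F category in all three interruption tables, and check it against the eCRF code list.

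The cost is SAP wording and minor programming, done before unblinding. No new collection should be needed, provided the diary or the dose adjustment form identifies the suspended days; this should be confirmed because neither form is shown. Reported days on drug can only stay the same or fall. No dosing rule changes.
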